### **Event Rates**

Summary tables will calculate endpoint event rates (e.g. new stroke, safety outcomes) per 3-month in the following way. The number of 4-week periods that the subject was on treatment for will be rounded up to the next integer. The number of events that a subject had will be divided by the number of 4-week periods, and then multiplied by 3, to give an event rate per 3-month e.g.;

- Number of 4-week periods = round up (number of weeks on treatment / 4)
- Number of event rate per 3-month =  $3 \times \text{number of events} / \text{no of 4-week periods}$ .

For example if a subject had 2 events then withdrew after 3 weeks of treatment

- Number of 4-week periods = round up (3/4) = round up (0.75) = 1
- Number of event rate per 3-mo =  $3 \times (\text{number of events} / \text{no of 4-week periods}) = 3 \times (2 / 1) = 6$ .

Using 1-month periods in this way means that it is not likely that a subject will have unreasonably high value, which could happen if it was assumed the rate per time was constant. In the example above assuming a constant rate would have lead to a value of 9 events per 3-month, whereas using this method leads to a value of 6 per year.

The average event rate for each treatment group will be calculated as: the sum of number of event for all the patients / the sum of number of 4-week treatment periods for all the patients.

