The treatment number will be allocated using a centralized treatment allocation system (Inter-voiceResponse System, IVRS) on D1 (baseline visit). Before randomizing a patient, the investigator will have to contact the IVRS and give some information (such as study number, patient date of birth and initials, study site, and time between symptom onset and randomization). A treatment number will then be given to the investigator, who will give the first box of the corresponding package to the patient.

**Primary Endpoint:** Percentage of patients with new stroke (ischemic or hemorrhage) at 3 months.

**Study Duration for Each Subject:** Each subject is followed for 90 days from randomization; the trial will be completed in 3 years.

**Number of Centers:** Up to a total of about 100 investigational sites in the China in Clinical Research Network.

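### The SAP's Event Rates rule gives wrong absolute stroke and safety rates in the summary tables: its group average is per 4 weeks, not per 3 months, and its rounding can charge a 90-day completer four periods

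*Supplement*

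**What the plan says.** The Event Rates section of the final SAP opens: "Summary tables will calculate endpoint event rates (e.g. new stroke, safety outcomes) per 3-month in the following way". It then gives three instructions.

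- Exposure: "The number of 4-week periods that the subject was on treatment for will be rounded up to the next integer".
- Per subject: "The number of events that a subject had will be divided by the number of 4-week periods, and then multiplied by 3".
- Per treatment group: "the sum of number of event for all the patients / the sum of number of 4-week treatment periods for all the patients".

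The worked example begins "For example if a subject had 2 events then withdrew after 3 weeks of treatment" and reaches 6. The section then compares this with a constant-rate calculation: "assuming a constant rate would have lead to a value of 9 events per 3-month, whereas using this method leads to a value of 6". The sentence ends by labelling the 6 as an annual figure: "whereas using this method leads to a value of 6 per year".

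The protocol synopsis states: "Each subject is followed for 90 days from randomization". The protocol's primary endpoint (synopsis and section 4.6.1) is the percentage of patients with a new stroke at 3 months. The SAP's primary analysis (Main Model) is Kaplan-Meier with a Cox hazard ratio.

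**The concern.** One section uses three time units: 3 months in the opening, 4 weeks in the group formula and a year in the example. The multiplier of 3 treats three months as three 4-week periods, or 84 days, while treatment is planned for 90 days. Rounding up can therefore charge a completer a fourth period.

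The denominator is time on treatment, although the tables are for the ITT population. The numerator counts every event, whereas the SAP's Time to Event Analysis uses the first.

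What is at stake is the absolute rates. Readers weigh strokes prevented against bleeds caused on the absolute scale. A programmer who followed this section would tabulate stroke rates that disagree with the Kaplan-Meier curve in the same report and with the protocol's percentage endpoint.

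The reach is not trivial. The secondary efficacy sections also ask for an event rate for each vascular component and a death rate by group, and Event Rates is the SAP's only section that defines how to compute an event rate.

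**Working it through.** **Inputs.** Rounding rule, factor 3 and group formula: SAP, Event Rates. Follow-up of 90 days: protocol synopsis. Final visit at Day 90 ± 7, so Days 83 to 97: protocol section 9.3. Illustrative rates of 0.14 and a 22% reduction, and 5% drop-out: SAP, Sample Size Considerations.

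**Step 1. Reproduce the SAP's example.** Two events, 3 weeks: round up (3/4) = 1, and 3 × 2/1 = 6, as stated. The constant-rate comparator of 9 follows from 2/3 × 13 weeks = 8.67, or 2 × 90/21 = 8.57. Twelve weeks would give 8. The comparator therefore takes three months as about 13 weeks or 90 days, while the multiplier takes it as 12 weeks.

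**Step 2. Completer with one event, weeks counted as fractions.** Periods = round up (days/28); rate = 3 × 1/periods.

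| Days on treatment | Days/28 | Periods | Rate per 3 months |
|---|---|---|---|
| 83 | 2.96 | 3 | 1.00 |
| 84 | 3.00 | 3 | 1.00 |
| 85 | 3.04 | 4 | 0.75 |
| 90 | 3.21 | 4 | 0.75 |
| 97 | 3.46 | 4 | 0.75 |

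At Day 90 the right value is 1/90 × 90 = 1.00. Every length from 85 to 97 days gives 0.75.

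**Step 3. Same subject, completed weeks.** Day 90 is 12 completed weeks; 12/4 = 3 periods; rate 1.00. Day 91 is 13 weeks; 13/4 rounds up to 4; rate 0.75. The step moves to Day 91, still inside the visit window.

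**Step 4. Group average, all treated 90 days.** The second arm's rate is 0.14 × 0.78 = 0.1092.

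| True rate per 3 months | Weeks counted as | Group formula as written | With factor 3 restored |
|---|---|---|---|
| 0.14 | fractions | 0.14/4 = 0.035 | 0.105 |
| 0.1092 | fractions | 0.1092/4 = 0.0273 | 0.0819 |
| 0.14 | completed | 0.14/3 = 0.047 | 0.14 |

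With fractional weeks the shortfall is 1 − 1/4 = 75% as written, if labelled per 3 months, and 1 − 3/4 = 25% with the factor 3. With completed weeks it is 1 − 1/3 = 67% as written and nil with the factor 3.

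**Step 5. Early stopping, fractional weeks.** Assume the SAP's 5% stop treatment uniformly over 90 days. Stoppers average (28×1 + 28×2 + 28×3 + 6×4)/90 = 2.13 periods, so the group mean is 0.95 × 4 + 0.05 × 2.13 = 3.91. The shortfalls become 1 − 1/3.91 = 74% and 1 − 3/3.91 = 23%. For a single early stopper the error is erratic: with one event, Day 28 scores 3.00 against an exact 90/28 = 3.21, but Day 29 scores 1.50 against 90/29 = 3.10.

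**Step 6. Ratio between arms.** With equal exposure the periods cancel and the ratio stays 0.78. In an extreme case, every stroke patient stops in the first period and everyone else has four. Mean periods are then 4 − 3 × 0.14 = 3.58 and 4 − 3 × 0.1092 = 3.672, and the ratio is (0.1092/3.672)/(0.14/3.58) = 0.76.

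**The case against.** **Only descriptive tables are involved.** This stands. The primary, composite, component and death analyses use Cox models, with Kaplan-Meier for stroke and the composite. Adverse events and deaths use Fisher tests. Nothing here changes alpha, power, p-values or hazard ratios. A reader might infer that all reported stroke and bleeding rates will be 25% to 75% too low, but the Kaplan-Meier stroke estimates will be reported too and are sound.

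**The 0.75 depends on an undefined unit.** This also stands. The SAP does not say whether weeks are fractional or completed, and its only example uses a whole number. Completed weeks give 1.00 at Day 90. That removes the Day-90 rounding error but not the missing factor 3 or the mixed units.

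**The missing factor 3 may be shorthand.** Possibly, since it appears twice just above. But the group formula is written out in full without it, under an opening sentence that promises rates per 3 months.

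**Three further inferences go beyond the documents.**

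- That this is the only SAP calculation reaching GUSTO bleeding: the Adverse Events section gives numbers and percentages of subjects by preferred term, which would capture bleeding reported as an adverse event, though not by GUSTO grade.
- That a number needed to treat would be misreported: the SAP derives none from these tables; its figure of 32 belongs to the sample-size section.
- That the treatment comparison is materially distorted: the extreme case in Step 6 moves the ratio only from 0.78 to 0.76. Stroke is not among the listed reasons for stopping study drug (protocol section 7.5.2).

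**Conclusion.** The rule is wrong as written and should be replaced. Its group average is per 4 weeks under a section that promises per 3 months, and its example carries a third unit; this holds however weeks are counted.

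The further 25% shortfall at Day 90 rests on fractional weeks. The 75% figure rests on fractional weeks and on printing the unscaled average as per 3 months. Both describe groups of completers measured against events per subject, and soften slightly to 23% and 74% under the Step 5 assumption.

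The damage is confined to absolute rates in the summary tables for stroke and safety outcomes. The primary test and the hazard ratios are safe, and the comparison between arms is nearly so when exposure is similar. It still warrants correction because these are key efficacy and safety endpoints and the rule is explicit enough to be programmed as it stands.

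**What to change.** Delete the 4-week rounding rule, the group formula and the worked example. For each endpoint the section covers, including GUSTO moderate or severe bleeding, report by arm the number of patients with an event and the Day-90 cumulative percentage from Kaplan-Meier with a 95% CI. This matches the protocol's percentage endpoint and extends what the SAP already plans for stroke.

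If an incidence rate is also wanted, define it as first events divided by total exact follow-up days, times 90, labelled per 90 days throughout. Use follow-up days rather than treatment days, so that stopping study drug does not change the denominator.

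Make the change before unblinding, since the SAP has the displays pre-programmed on dummy treatment codes. The cost is SAP wording and simpler programming; sample size, data collection and the primary test are untouched.

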### **Time to Event Analysis**

Differences between treatments in the risk of new stroke (ischemic or hemorrhagic) event and combined vascular events during maximum 90-day follow-up were assessed using standard Kaplan-Meier time-to-event approaches. The time to the first event was used in the model when there were multiple events of the same type. Patients were considered censored at the time of study termination or death if there were no events occurred during the study.

## **Study Population**

### **Disposition of Subjects**

The number of subjects in each analysis population will be presented, subjects to be excluded from the Per Protocol population will be listed, and the total number of subjects attending each clinic visit will also be summarized by treatment group.

The number of subjects Randomized, completed and prematurely withdrawn from the study will be presented for each treatment group. The primary reasons for withdrawal both prior to and post randomization will also be presented.

A data display listing and summary of deviations from the inclusion/exclusion criteria will be presented for all subjects who were either entered or Randomized into the trial.

### Protocol Deviations

Subject data will be examined for evidence of protocol violators in order to assess how well the protocol was followed. Inclusion and exclusion criteria are detailed in the study protocol.

Subjects who commit protocol violations will be included in the ITT Population but excluded from the Per Protocol Population. These protocol violations will be shown in a listing. Subjects can either be full or partial protocol violators. A full protocol violator is completely excluded from the Per Protocol Population. A partial protocol violator has only some data excluded. For subjects who violated the protocol during the treatment period due to unpermitted changes in the medication or prohibited concurrent medication, the analysis will only use data recorded prior to the violation.

For all violations which reference the treatment period, the treatment start date will be used as the reference date.

A listing of all possible protocol violators will be produced for clinical review. The final list of subjects who are protocol violators and are therefore excluded from the Per-Protocol population will be agreed by the study team prior to unblinding the study.

### Demographic and Baseline Characteristics

The following demographic information will be listed and summarized for subjects in each treatment group: age, sex, body mass index (BMI). This will also be done for smoking history, stroke and TIA history, symptoms of the index event, past medical history, family history, alcohol use, pretreatment Rankin Score and NIHSS score.

Laboratory tests will be listed and summarized for subjects in each treatment group including serum creatinine, glycemia, neutrophil count, and platelet count.

Vital signs including supine systolic blood pressure, diastolic blood pressure, and heart rate will also be listed and summarized in each treatment group.

Qualifying TIA baseline ABCD score will be summarized by treatment group.

### Treatment Compliance

The overall percentage compliance will be calculated separately for the doses taken for clopidogrel/ASA and ASA alone group using the following formula:

$$\frac{\text{Actual number doses taken}}{\text{Expected number of doses to be taken}} * 100$$

Where expected number of doses taken = [treatment stop date - treatment start date + 1].

This data will be listed and summarized for all subjects by treatment group, in addition the number and percent of subjects falling into the following categories will be presented: <20%, 20-<50%, 50-<80% and ≥80%.

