#### **3.2 Secondary**

3.2.1. To assess the secondary composite outcome: composite of any stroke, myocardial infarction, and vascular death.

3.2.2. To assess the primary outcome measure in a Per-protocol (PP) population. This will include all patients who have not had a significant interruption of study drug (Actual number doses taken less than 80% of expected number of doses taken) or major protocol violation.

3.2.3. To assess separately the effects of this Clopidogrel regimen versus ASA alone on the incidence of: new clinical vascular events (ischemic stroke/ hemorrhagic stroke/ TIA/ MI/ vascular death) as a cluster and evaluated individually.

3.2.4. To evaluate change in modified Rankin Scale [mRS,(continuous)] and percentage with score 0-2 at last follow-up.

3.2.5. To compare the safety of the two treatment regimens in terms of:

- ✧ Severe or moderate bleeding (GUSTO definition, see appendix)
- ✧ Intracranial hemorrhage
- ✧ Total mortality
- ✧ AEs/SAEs
  - Thrombotic thrombocytopenic purpura (TTP)
  - Granulocytopenia
  - Hypersensitivity
  - Renal failure

3.2.6. To compare efficacy and safety by etiology, non-Intracranial artery diseases (non-ICAD) vs. ICAD (substudy)

3.2.7. To compare efficacy and safety by qualifying event, TIA vs. minor stroke.

3.2.8. To compare efficacy and safety in those previously taking ASA or Clopidogrel at presentation or not.

3.2.9. To compare efficacy and safety by gender and age (<65 years vs ≥65 years).

3.2.10. In further exploratory analysis, to evaluate impairment (change in NIHSS scores), and Quality of Life (EuroQol EQ-5D scale) among survivors.

3.2.11. To compare efficacy and safety by time to randomization, < 12 hours vs. ≥ 12 hours.

3.2.12. To evaluate the primary outcome and intracranial hemorrhage in those with and without imaging evidence of infarction on the initial head CT or MRI imaging.

---

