**Patient box including box 1 and box 2**

Box 1 composed of two wallets: the first one is non-open-label clopidogrel or placebo clopidogrel (C1) containing 75mg \* 7 pills \* 4 pieces for period from Day 1 to Day 21 ± 2. The other one is non-open-label ASA (A1) containing 25mg \* 30 pills \* 2 piece + 6 pills for period from Day 2 to Day 21 ± 2.

Box 2 composed of two wallets for period from Day 21± 2 to Day 90± 7: the first one is non-open-label clopidogrel or placebo clopidogrel (C2) containing 75mg \* 7 pills \* 11 pieces. The other one is non-open-label ASA or placebo ASA (A2) containing 25mg \* 30 pills \* 8 pieces.

The content of the labeling will be in accordance with the local regulatory specifications and requirements.

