#### **7.4.3 Treatment Accountability and Compliance**

Compliance will be assessed by counting returned tablets at each visit.

The investigator (or delegates) will complete the appropriate page of the CRF or study drug inventory log form.

The date of study drug interruption must also be recorded.

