## Study Objective(s) and Endpoint(s)

### Study Objective(s)

The primary objective of this study is to assess the effects of a 3-month regimen of clopidogrel initiated with a loading dose of 300 mg followed by 75 mg/day combined with aspirin 75 mg/day during the first 21 Days versus a 3-month regimen of aspirin 75 mg/day alone on reducing the 3-month risk of any stroke (both ischemic and hemorrhagic) when initiated within 24 hours of symptom onset in high-risk patients with TIA or minor ischemic stroke.

The secondary objectives of this study are:

- To assess the secondary composite outcome: composite of any stroke, myocardial infarction, and vascular death
- To assess separately the effects of this Clopidogrel regimen versus ASA alone on the incidence of: new clinical vascular events (ischemic stroke/ hemorrhagic stroke/ TIA/ MI/ vascular death) as a cluster and evaluated individually.
- To assess whether there are differential treatment effects in predefined subgroups:
  - ✧ (<65 years vs ≥65 years)
  - ✧ Sex (male vs female)
  - ✧ Index event (minor stroke vs TIA)
  - ✧ TIA risk stratification ( $ABCD^2=4$  vs  $ABCD^2>4$ )
  - ✧ Previous stroke
  - ✧ Previous TIA
  - ✧ History of hypertension
  - ✧ History of diabetes
  - ✧ Systolic blood pressure at baseline (<140mmHg vs ≥140mmHg)
  - ✧ Time to randomization (<12 hours vs ≥12 hours)
  - ✧ Aspirin taken within 24h
- To assess the primary outcome measure in a Per-protocol (PP) population. This will include all patients who have not had a significant interruption of study drug (less than a total of 10 days off study drug) or major protocol violation.

Other objectives are:

- To evaluate treatment differences if changes in modified Rankin Scale from baseline to the last follow-up.
- To compare the safety of the two treatment regimens in terms of:
  - ✧ Severe or moderate bleeding (GUSTO definition)
  - ✧ Intracranial hemorrhage
  - ✧ Total mortality
  - ✧ AEs/SAEs

- In further exploratory analysis, to evaluate treatment differences of impairment (change in NIHSS scores), and Quality of Life (EuroQol EQ-5D scale) among survivors.

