## **General considerations for data analyses**

All programming will be performed using SAS Version 9.0. All analysis output will use the following treatment group naming conventions and treatment order:  
clopidogrel /ASA for a loading dose of clopidogrel 300mg followed by clopidogrel 75 mg /day day 2-90 plus blinded aspirin 75 mg once /day day 2-21 and then aspirin placebo day 22-90  
ASA for clopidogrel placebo on day 1, followed by aspirin 75 mg/day plus clopidogrel placebo day 2-90  
Unless otherwise specified all significance tests will be 2-sided at the  $\alpha=0.05$  level and all confidence intervals will be 95%.

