### Extent of Exposure

The extent of exposure will be calculated as the number of days between start of treatment and end of treatment (i.e. treatment stop date – treatment start date + 1), and categorized into months: <1, 1-2, 2-3 months. Exposure will then be summarized by treatment group.

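### The SAP's compliance formula gives 100% to patients who take every dose and then stop early, and the protocol and SAP set different per-protocol adherence rules

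*Supplement*

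**What the plan says.** **Compliance.** The final SAP, Treatment Compliance, divides doses taken by doses expected and defines the latter: "Where expected number of doses taken = [treatment stop date - treatment start date + 1". Patients are then tabulated in the bands "<20%, 20-<50%, 50-<80% and ≥80" per cent. The same date expression is used under Extent of Exposure, where the result is "categorized into months: <1, 1-2, 2-3 months".

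**Per-protocol adherence.** The final protocol, 3.2.2, keeps patients without a "significant interruption of study drug (Actual number doses taken less than 80% of expected number of doses taken". The final SAP, Study Objective(s), describes the same population with "significant interruption of study drug (less than a total of 10 days off study drug". The SAP's Per Protocol population section refers only to patients in the ITT population who are not protocol violators and gives no adherence threshold. That section and Protocol Deviations add that a partial violator contributes data up to the violation.

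**Units.** Protocol 7.4.3 says "Compliance will be assessed by counting returned tablets at each visit". Protocol 6.2 and 6.4 describe 75 mg aspirin tablets, one a day. Protocol 7.2 describes the packs differently: "The other one is non-open-label ASA (A1) containing 25mg".

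**The concern.** The compliance denominator ends when the patient stops. Permanent discontinuation is a main form of non-adherence, and this formula cannot register it. A table built this way can show nearly everyone at 80% or above while a sizeable group took a small part of the course.

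The per-protocol analysis of the primary outcome is a stated objective in both documents, and its membership must be settled before unblinding. With two adherence rules in force, two programmers working from the current texts could build different sets. The SAP also does not say whether days after a permanent stop count as days off drug. Under one reading, therefore, the same early stopper is kept by one rule and removed by the other.

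**Working it through.** The plan states no compliance figure to reproduce, so this is direct arithmetic on its definitions.

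**Inputs**
- Denominator: stop date minus start date plus 1 (SAP, Treatment Compliance).
- Meaning of stop date: the patient's own. Under Extent of Exposure the same expression yields durations below one month, which a planned Day 90 could not.
- Planned course: 90 days (SAP, General considerations: "followed by aspirin 75 mg/day plus clopidogrel placebo day 2-90"). The final visit is D90±7 (protocol 9.3), so 83 to 97 days.
- Per-protocol rules: below 80% of expected doses is out (protocol 3.2.2); under 10 days off drug is in (SAP objectives).

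**1. Early stoppers who missed nothing before stopping**

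For a stop on day *s*, the SAP score is *s*/(*s* − 1 + 1) = 100%. The share of the planned course is *s*/90.

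| Stop day | SAP score | Share of 90 days |
|---|---|---|
| 5 | 5/5 = 100% | 5/90 = 5.6% |
| 10 | 100% | 11.1% |
| 21 | 100% | 23.3% |
| 30 | 100% | 33.3% |
| 45 | 100% | 50.0% |
| 60 | 100% | 66.7% |

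Missed doses before the stop still count. A Day 30 stop with 7 missed scores (30 − 7)/30 = 76.7%, against 23/90 = 25.6% of the course.

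**2. The two per-protocol rules on one scale**

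| Course length | Most days missed at ≥80% | Most days missed at <10 off | Days off that give opposite answers |
|---|---|---|---|
| 83 | 16 | 9 (89.2% taken) | 10 to 16 |
| 90 | 18 | 9 (90.0%) | 10 to 18 |
| 97 | 19 | 9 (90.7%) | 10 to 19 |

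**3. One patient under both rules**

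Take a patient who has every dose to Day 5 and then stops for good.
- 80% rule with the SAP's denominator: 5/5 = 100%, in.
- 80% rule with a 90-day denominator: 5.6%, out.
- 10-day rule, if days after the stop count as off drug: 90 − 5 = 85 days off, out.
- 10-day rule, if they do not: 0 days off, in.

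**4. Units**

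The formula expects one dose per day, while the raw data are tablets. Day 1 has four clopidogrel tablets (protocol 6.4). If tablets were used as doses, full adherence would give (4 + 89)/90 = 93/90 = 103.3%. Aspirin tablets cannot be converted to doses until protocol 6.2 and 6.4 agree with 7.2.

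**The case against.** The strongest reply is that the formula measures adherence while on treatment, a legitimate quantity, and that duration is reported separately under Extent of Exposure, with withdrawals covered under Disposition of Subjects and Time to withdrawal. That stands in part: early stopping is not hidden from the report as a whole. But the compliance section calls its figure overall compliance and does not present it as an on-treatment measure.

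Next, the SAP does not tie this formula to per-protocol membership. Protocol 3.2.2 leaves expected doses undefined, and the Chinese text of 3.2.2 sets the 80% against the expected total, which fits a planned course. This also stands. The early stopper is kept under the 80% rule only if the SAP's denominator is borrowed for it. Since the SAP supplies the only written definition of expected doses, that borrowing is likely enough to need ruling out.

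A reader might infer that the 10-day rule deletes patients because they had a primary stroke. The documents do not establish this. It requires that off-drug days after an event count and that stopping makes the patient a full violator, and the SAP says neither. The partial-violator provision could keep the event, since the stroke precedes the stop. However, Protocol Deviations applies that provision to unpermitted medication changes and prohibited drugs, and nothing links it to the 10-day rule. Nor can a number of lost events be given: no document states how often stroke leads to stopping, and protocol 7.5 asks that drug be continued where possible.

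A reader might also divide a count of 25 mg pills by days and get a very large percentage. The SAP's numerator is doses, so the text does not direct that calculation.

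Finally, 10 days is not arbitrary: protocol 7.5.1 uses under 10 days for temporary discontinuation. Which threshold to adopt is therefore open. That there are two is the fault.

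**Conclusion.** The point holds in two parts. The SAP's denominator scores a patient who is fully adherent until a permanent stop at 100% whatever the stop day, against 5.6% to 66.7% of a 90-day course for stops on Days 5 to 60. And protocol 3.2.2 and the SAP objectives give different per-protocol sets: on 90 days, patients with 10 to 18 days off are in under one and out under the other, with no threshold in the SAP's population section to decide.

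Exclusion of patients because of a primary stroke is a possibility that the wording leaves open, not a demonstrated effect.

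This rests on two readings. The stop date is taken as the patient's own, because of its use under Extent of Exposure; it is not defined in words. The SAP's parenthesis is taken to mean that under 10 days off qualifies for inclusion; read literally after the words it follows, it would define a significant interruption as a short one.

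The reach is limited to the compliance table and the secondary per-protocol analysis. The primary ITT analysis is untouched.

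**What to change.** 1. State one per-protocol adherence rule, in the same words, in protocol 3.2.2 and in the SAP's objectives and Per Protocol population sections. At least 80% of scheduled doses would do and matches the SAP's own top compliance band. Require it for both the clopidogrel and the aspirin component, active or placebo.
2. Define expected doses as those scheduled from Day 1 (Day 2 for blinded aspirin, whose Day 1 dose is open label) to the earliest of the scheduled end of treatment, death or first primary event, and not to the actual stop date. Take the scheduled end as the D90±7 final visit, or Day 90 if that visit is missed; a fixed Day 90 would score a fully adherent patient treated to Day 97 at 97/90 = 107.8%. Ending at the first primary event means that off-drug time after a stroke cannot remove that stroke from the analysis.
3. Count doses, not tablets: the four clopidogrel tablets on Day 1 are one dose. Reconcile the 25 mg aspirin packaging in protocol 7.2 with the 75 mg tablets in 6.2 and 6.4 before returned tablets are converted to doses.
4. If adherence while on treatment is also wanted, keep the present formula as a separately labelled line.

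The cost is wording in two documents and one changed derivation. No new data are needed. Reported compliance will be somewhat lower.
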